8.1.3 EXEMPTED ADVERSE EVENTS

Adverse Events do not include:

- Medical or surgical procedures; the condition that leads to the procedure is the adverse event
- Pre-existing disease or a condition present before treatment that does not worsen

8.1.4 OTHER NOTABLE EVENTS

Notable adverse events which impact on the injection schedule and therefore require expedited (within 24 hours of the investigator becoming aware of the event) reporting whether or not they meet the serious criteria include:

- Grade 3 (severe) and above solicited adverse events which last more than 72 hours and Grade 3
 and above laboratory adverse events that are confirmed on repeat testing if possible
- Any adverse event leading to a clinical decision to interrupt or discontinue the injection schedule
- Pregnancy within 18 weeks of an injection

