- 9. At 48 (-/+5) hours post-vaccination the team will call the fourth participant and go through their diaries. If the reactions are Grade 1-2, or transient Grade 3 that resolve within 24 hours, the fifth participant may receive 5 μ g of LNP-MARVsaRNA plus 4 μ g of LNP-EBOVsaRNA plus 4 μ g of LNP-LASSAsaRNA

- 10. At 1 day post immunisation, the fifth participant will attend the trial site to review AEs and donate blood to measure innate immune responses.
- 11. At 48 (–/+5) hours post-vaccination the team will call the fifth participant and go through their diaries. If the reactions are Grade 1-2, or transient Grade 3 that resolve within 24 hours, the dose evaluation cohort of remaining 35 participants may start to be enrolled and randomised into one of the 5 groups to receive their first immunisation.
- 12. Sentinel participants will be evaluated again as above after receiving their second dose. If the reactions are Grade 1-2, or transient Grade 3 that resolve within 24 hours, the cohort of remaining 35 participants may receive their second dose

The steps above describe the fastest plan to enrol into the 5 groups and is justified based on previous experience with this self-amplifying RNA platform. However, if there are persistent Grade 3 reactions observed in any of the sentinels, the team will invite the affected participant to attend the trial site in order to evaluate these and will proceed to vaccinate a second sentinel within the same group. The group will not be changed until at least 1 participant has provided acceptable safety data to at least 48 (–/+5) hours post-vaccination. If 2 or more of the participants at any dose level in this part of the trial have persistent Grade 3 (or worse) reactions, or if 1 or more has a serious adverse reaction, the dose will not be expanded, and the trial stopping rules described below (7.1.5) will be triggered.

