7.1.5 Dose Modifications For Toxicity & Schedule Interruptions

Target visit dates (based on the enrolment date) should be adhered to as far as possible, based on the allowable window (detailed in Table 2). The schedule may be interrupted if a participant has symptoms or signs on the day of scheduled injection, and the investigator considers it best to defer the injection. A temperature over 37.5°C would prevent injection on the day. Clinicians should consult the PI/Medical Delegate if there are any Grade 1 (mild) symptoms or signs listed in **Table 4**. The participant will be asked to return for review within the ideal window period of the scheduled injection. Provided the injection is administered during the window period outlined in the paragraph below for missed visits, this will not be a protocol deviation.

The PI or Medical Delegate should interrupt the vaccine schedule and inform the Chief Investigator within 24 hours using the safety email if there is a confirmed:

Grade 3 (severe) or worse solicited adverse event that has persisted for more than 72 hours regardless
of relationship

or

- other Grade 3 (severe) or worse adverse event that is possibly, probably or definitely related to vaccine or
- serious adverse reaction regardless of grade

The Chief Investigator/Delegate may recommend further investigations or referral to an independent expert to support the clinical management of the participant. Such events are highly likely to result in discontinuation, but a decision to resume will be taken by the PI with the participant, and only with the approval of the independent members of the TSC.

Injections for all participants will be paused pending a review of all safety data by the Trial Steering Committee if two participants out of 20, and the equivalent (10%) thereafter develop persisting Grade 3 (severe) adverse reactions within 7 days of immunisation, or any participant experiences a serious adverse reaction at any time. Approval of an amendment from the competent authorities is required before the trial can be resumed.

If two participants in any Group experience a Grade 3 reaction the trial will be paused and only resumed after approval of a substantial amendment.

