11. MONITORING

The trial will be overseen by a Trial Steering Committee (TSC), which will include membership independent of the Trial Management Group (TMG). The reason for this is the need for real-time assessment of the safety data. The TSC will be informed by the Chief Investigator when the first participant receives the first injection of 5 μg, and a report of 7-day reactogenicity will be provided when the first 4 individuals have completed their Week 1 visit (see Section 4.1.1). The TSC will receive weekly progress reports. Weekly reports will continue whilst day 7 data are accumulating; after which point the frequency will be determined by the TSC (in accordance with the TSC Charter). Any adverse reactions that lead to interruption in the schedule for an individual or plan for enrolments described in Section 7.1.4 will be immediately reported to the TSC. The site will be requested to notify the Chief Investigator within 24 hours of any adverse reaction that is a cause for concern as described in Section 8. These reports will be shared with the Trial Steering Committee immediately. If there are 2 out of 8 participants (25% thereafter) who experience similarly severe adverse reactions, vaccinations will be paused in all individuals and the competent authority informed. The TSC will be asked to review the accumulating safety data from all participants and make a recommendation about resuming vaccinations.

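### The group pause in Section 7.1.5 counts Grade 3 reactions of any duration, but the protocol names solicited Grade 3 events for 24-hour reporting only beyond 72 hours

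*Protocol*

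**What the plan says.** **What triggers a pause.** Section 7.1.5 has a group rule: "If two participants in any Group experience a Grade 3 reaction the trial will be paused", and the trial resumes only after a substantial amendment is approved. No duration is attached. The whole-trial rule just before it (two of the first 20 participants, then 10%) counts only participants who "develop persisting Grade 3 (severe) adverse reactions within 7 days of immunisation".

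**What must reach the Chief Investigator within 24 hours.** Section 7.1.5 lists three confirmed categories:
- a "Grade 3 (severe) or worse solicited adverse event that has persisted for more than 72 hours", whatever its relationship to vaccine;
- any "other Grade 3 (severe) or worse adverse event that is possibly, probably or definitely related to vaccine";
- a serious adverse reaction of any grade.

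Section 8.1.4 lists notable events for expedited reporting. The solicited item is "Grade 3 (severe) and above solicited adverse events which last more than 72 hours". A further item covers any event that leads to a clinical decision to interrupt or stop injections.

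**Other routes.** Section 11 asks the site to "notify the Chief Investigator within 24 hours of any adverse reaction that is a cause for concern as described in Section 8" and passes those reports to the TSC at once. It also says "The TSC will receive weekly progress reports". Section 9.4 has Grade 3 diary events flagged in the EDC system so that an early visit can be arranged. Section 4.1.1 treats short Grade 3 reactions in sentinels as acceptable: if reactions are Grade 1-2 or "transient Grade 3 that resolve within 24 hours, the dose evaluation cohort of remaining 35 participants may start".

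**The concern.** A pause rule works only if the events it counts are reported promptly. Here the reporting threshold that is spelled out for solicited events (more than 72 hours) sits above the pause threshold (any duration). A solicited Grade 3 fever that settles in two days counts as one of the two reactions that stop the trial. Yet on a plain reading of Section 8.1.4 and the first bullet of 7.1.5, it need not be notified within 24 hours.

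If a site worked to the 72-hour limit, the first such reaction in a group might reach the Chief Investigator only in the next weekly report. Should a second participant in the group react before then, the pause condition would be met while dosing went on. This is a first-in-human trial, and two groups receive 9 µg and 13 µg of saRNA in total, so the rule should not depend on how one bullet is read.

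**Working it through.** The protocol gives no figure on this point, so there is none to reproduce. The check is mainly a comparison of texts.

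**Step 1. Does the group rule imply persistence?** The neighbouring whole-trial rule states it and the group rule does not. Section 4.1.1 also distinguishes transient from persistent Grade 3. Section 11 describes a pause at 2 of 8 for reactions of similar severity to those it has just discussed, without settling duration. As written, the 7.1.5 group rule counts short reactions.

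**Step 2. Does any text expressly require 24-hour notice of a short solicited Grade 3 reaction?**
- 7.1.5 first bullet: no; more than 72 hours is required.
- 7.1.5 second bullet: ambiguous. If *other* means anything not caught by the first bullet, it covers related short solicited reactions. If it means not solicited, it does not.
- 8.1.4: no for the solicited item. The item on decisions to interrupt applies only if the second bullet of 7.1.5 is read broadly.
- Section 11: refers back to Section 8, so it inherits the same question.
- 9.4: the flag covers every Grade 3 diary event, but names neither the Chief Investigator, a 24-hour limit nor a count by group.
- 8.2: same-day entry on the AE form, which is recording rather than escalation.

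**Step 3. How long could recognition lag?** Reports are weekly during vaccination weeks (Sections 11 and 13.1), so the wait is between 0 and about 7 days.

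**Step 4. How many more could be dosed?** Assume enrolment in 3 months (13 weeks) and about 10 days for five sentinels at 48-hour steps. The other 35 are then dosed over 13 − 10/7 = 11.6 weeks, or 35/11.6 = 3.0 per week. A full-week delay means about 3 further participants; a half-week delay about 1.5. If enrolment took 6 weeks (an assumption), 35/6 = 5.8 per week gives about 6 and 3.

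**Step 5. How likely is the rule to be met at all?** Table 5 shows 2 of 24 participants with a systemic Grade 3 event at 5 µg and no local Grade 3, so p = 2/24 = 8.3%. With independent participants and a common rate:
- one group of 8: 1 − (22/24)^8 − 8(2/24)(22/24)^7 = 13.9%;
- at least one of five groups: 1 − (1 − 0.139)^5 = 52.7%.

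At the 11% reported in Section 3.1.6.2 for 10 µg, the figures are 21.7% and 70.6%. These are chances of a pause, not of a late pause.

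**Step 6. Why no chance of delay is given.** It needs the share of Grade 3 reactions lasting 72 hours or less, and the share not otherwise notified. The protocol gives neither. A worst case sets both to 100% and the lag to a full week:
- two of 7 non-sentinels or more react: 11.0% at p = 2/24;
- two given participants are dosed within a week of each other: 1 − (1 − 1/11.57)² = 16.5%;
- product: 1.8% per group; any of five groups: 1 − (1 − 0.018)^5 = about 9% in the first-dose round.

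A half-week lag roughly halves this. It is a worst case at that rate and enrolment pace, not an estimate.

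**The case against.** The best reply is that Section 7.1.5 already covers the case. Only a reaction counts towards the group pause, and Table 6 defines a reaction as an event possibly, probably or definitely related. The second bullet requires 24-hour notice of other Grade 3 events with exactly that relationship. The first bullet still has a job, because it applies whatever the relationship: persistent solicited events even if unrelated, everything else if related. Section 4.1.1 does not contradict this, since it governs dosing of the next participants, not the affected person's own schedule.

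Nor is the Chief Investigator clearly a bottleneck. The pause does not depend on notice to that person. There is one centre, its staff know the allocation, Grade 3 diary entries are flagged, and the Trial Management Team that prepares safety reports includes both the Chief Investigator and staff of the clinical research facility. Section 11.1 also foresees a Safety Reporting Plan, which is not at hand and might set alert recipients.

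Most of this stands and lowers the weight of the point. It does not remove the ambiguity. On the broad reading, the 72-hour limit in 8.1.4 would matter only for unrelated solicited events, which that item does not say, and every related transient Grade 3 reaction would interrupt the participant's schedule. A careful site could read the text either way.

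A reader might go further and infer that no text could require prompt notice of a short reaction. The second bullet of 7.1.5 shows that this is too strong.

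**Conclusion.** The mismatch is real: the group pause counts Grade 3 reactions of any duration, while the reporting text that names solicited events starts beyond 72 hours, and the one bullet that could close the gap is ambiguous. The consequence is small. Recognition of a pause could be late by a few days, at most about a week. That needs the narrow reading, two affected group-mates close together in time, and site staff who do not make the link themselves. At most about 3 further participants would be dosed meanwhile (about 6 if enrolment took 6 weeks).

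Two stronger inferences are not supported. The 53% is the chance that the rule is met in at least one group at the Table 5 rate; it says nothing about lateness. The 9% rests on every reaction being short, none otherwise notified and every report a full week away, none of which the protocol states. All these figures also assume independence and one rate across groups, although groups 4 and 5 receive more RNA. This is a low-priority but cheap improvement.

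**What to change.** Choose one of two.

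- **If every Grade 3 reaction is meant to count:** require notice to the Chief Investigator within 24 hours of any Grade 3 or worse reaction regardless of duration, with a running count by group. The simplest way is to add the Chief Investigator as a recipient of the existing Section 9.4 EDC flag.
- **If only persistent reactions are meant to count:** state the same duration in the 7.1.5 group rule and in 8.1.4, consistent with Sections 4.1.1 and 11. The sponsor would have to choose that duration, since 4.1.1 uses 24 hours and the reporting text uses 72.

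Leave the criteria for interrupting an individual's injections as they are. Relaxing them for transient reactions could loosen a safety rule and is not needed here.

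The cost is a wording change and one more alert recipient. Among 40 participants, expected Grade 3 reactors number 40 × 1/24 = 1.7, 40 × 2/24 = 3.3 and 40 × 0.11 = 4.4. That is about 2 to 4 extra notices at most, because reactions beyond 72 hours are already notified. The 1/24 is the rate of Grade 3 temperature in Table 5. The table does not say whether its rates cover one dose or both.

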8.1.5 PREGNANCY

Pregnancy is not an adverse event. However, any pregnancy that occurs during the conduct of the study and for 18 weeks after the last vaccination in a female participant or the partner of a male participant must be reported and followed to outcome and for six months after delivery to determine if a serious adverse event is observed. It should be reported to the Sponsor (Imperial College London) within 24 hours of the investigator becoming aware of a pregnancy. The pregnancy should be reported using the Notable Event form and Pregnancy form in the EDC system. Collecting information about the outcome from partners is subject to consent from the partner.

In the event of a pregnancy in a female participant, injections will be discontinued.

All Notable events, including pregnancy must be reported immediately using the EDC system. Under no circumstances should this exceed 24 hours following knowledge of the event.

8.2 Causality

All non-serious AEs and ARs, whether expected or not, should be recorded in the participants' medical notes and reported on the AE form in the EDC system on the day of the visit from screening through to the last trial visit for each subject.

SAEs and SARs should be notified to the sponsor (Imperial College London) within 24 hours of the investigator becoming aware of the event via the EDC system Under no circumstance should this exceed 24 hours following knowledge of the SAE or SAR. Immediate reporting should allow the sponsor to take the appropriate measures to address any potential new risks in the trial.

Participants must be followed up until clinical recovery is complete and laboratory results have returned to normal or baseline, or until the event has stabilised. Follow-up should continue after completion of the protocol if necessary.

8.2.1 SERIOUSNESS

When an AE or AR occurs, the investigator responsible for the care of the patient must first assess whether or not the event is serious using the definition given in **Table 4**. If the event is serious, then an SAE details must be entered in the EDC system within 24 hours. If the event is not an SAE but meets the notable event criteria (see section 8.1) complete a Notable Event Form and forward the report within 24 hours via the same mechanism.

8.2.2 SEVERITY OR GRADING OF ADVERSE EVENTS

The severity of all AEs and/or ARs (serious and non-serious) in this trial should be graded using the FDA: Toxicity Grading Scale for Healthy Adult and Adolescent Volunteers Enrolled in Preventive Vaccine Clinical Trials.

8.2.3 CAUSALITY

The investigator must assess the causality of all events in relation to the trial therapy using the definitions in **Table 6**. There are five categories: unrelated, unlikely, possible, probable, and definitely related. If the causality assessment is unrelated or unlikely to be related, the event is classified as an unrelated AE. If the causality is assessed as possibly, probably or definitely related, then the event is classified as an AR.

The investigator will also be asked to record concomitant medications and to assess the relationship of the event to each of these. If a serious adverse event is considered related to a concomitant medication, the investigator should report this to the MHRA via a yellow card.

8.2.4 EXPECTEDNESS

If there is at least a possible involvement of any trial treatment given to the participants, the Chief Investigator, on behalf of the Sponsor, will make an initial assessment of the expectedness of each SAR. An unexpected serious adverse reaction is one not previously reported in the current Reference Safety Information, which is in the LNP-MARVsaRNA/LNP-EBOVsaRNA/LNP-LASSAsaRNA Investigator's Brochure. A SAR that is more frequent or more severe than stated in the reference safety information would also be considered to be unexpected. If an SAR is assessed as being unexpected, it becomes a SUSAR.

Table 6: Assigning Type of AE Through Causality

RELATIONSHIP	DESCRIPTION	TYPE OF EVENT
Definitely	There is clear evidence to suggest a causal relationship and other possible contributing factors can be ruled out.	AR
Probable	There is evidence to suggest a causal relationship and the influence of other factors is unlikely.	AR
Possible	There is some evidence to suggest a causal relationship (for example, because the event occurs within a reasonable time after administration of the trial medication). However, the influence of other factors may have contributed to the event (for example, the patient's clinical condition, other concomitant treatments).	AR

Unlikely	There is little evidence to suggest that there is a causal relationship (for example, the event did not occur within a reasonable time after administration of the trial medication). There is another reasonable explanation for the event (for example, the patient's clinical condition, other concomitant treatment).	Unrelated AE
Unrelated	There is no evidence of any causal relationship	Unrelated AE

If an AE is considered to be related to trial treatment and the injections are interrupted please refer to Section 7.1.4.

8.3 Reporting Procedures

All adverse events should be reported. Depending on the nature of the event the reporting procedures below should be followed. Any questions concerning adverse event reporting should be directed to the trial coordination centre in the first instance. A flowchart is given below to aid in the reporting procedures (Figure 3).

8.3.1 Non-serious AR/AEs

All such toxicities, whether expected or not, should be recorded in the toxicity section of the relevant case report form and sent to the trial coordination centre within one month of the form being due.

8.3.2 **SERIOUS AR/AES**

Fatal or life-threatening SAEs and SUSARs should be reported on the day that the local site is aware of the event. The SAE form asks for nature of event, date of onset, severity, corrective therapies given, outcome and causality (i.e. unrelated, unlikely, possible, probably, definitely). The responsible investigator should sign the causality of the event. Additional information should be sent within 5 days if the reaction has not resolved at the time of reporting.

8.3.3 **SAEs**

An SAE form should be completed and faxed to the trial coordination centre for all SAEs within 24 hours. However, relapse, death and hospitalisations for elective treatment of a pre-existing condition do not need reporting as SAEs.

8.3.4 **SUSARs**

In the case of suspected unexpected serious adverse reactions, the staff at the site should:

Complete the SAE case report form & send it immediately (within 24 hours,), signed and dated to the trial coordination centre together with relevant treatment forms and anonymised copies of all relevant investigations.

Or

Contact the trial coordination centre by phone and then send the completed SAE form to the trial coordination centre within the following 24 hours as above.

The trial coordination centre will notify the MHRA, REC and the Sponsor of all SUSARs occurring during the trial according to the following timelines; fatal and life-threatening within 7 days of notification and non-life threatening within 15 days. All investigators will be informed of all SUSARs occurring throughout the trial.

The minimum criteria required for reporting an SAE are the participant's trial number and date of birth, name of investigator reporting, the event, and why it is considered serious.

The SAE details should be entered in the EDC system by an investigator (a clinician named on the Signature List and Delegation of Responsibilities Log, who is responsible for the participant's care), with due care being paid to the grading and causality, as outlined above. In the absence of the responsible investigator, the data should be entered by a member of the site trial team. The responsible investigator should subsequently check the SAE details on the EDC system, make changes as appropriate, as soon as possible.

Follow up details on the SAE should be entered in the EDC system as they become available. Extra, annotated information and/or copies of test results may be provided separately and can be emailed securely. The participant must be identified by trial number, month and year of birth and initials only. The participant's name should not be used on any correspondence and should be deleted from any test results.

Figure 3. Safety reporting flowchart

SAFETY REPORTING OVERVIEW Adverse Event Serious Not serious Seriousness Serious Adverse Event Adverse Event Related Not related Related Not related Causality to IMP to IMP to IMP to IMP Serious Serious Adverse Adverse Adverse Adverse Reaction Event Reaction Event (AR) (AE) (SAR) (SAE) Record in AR SAE notes + CRF Expectedness Expected Not Expected ΔF Record in notes + CRF + SAE form Suspected Serious Report to Sponsor Immediately? Unexpected Serious Adverse Serious **EXPEDITED REPORTING!** Reaction Adverse Record in notes + CRF + SAE form (SSAR) Reaction Report to Sponsor Immediately* (SUSAR) **SSAR** Report to MHRA & EC (7/14 days) Include in DSUR Record in notes + CRF + SAE form Report to Sponsor Immediately Include in DSUR

^{*} Unless identified in the protocol as not requiring immediate reporting

SAE REPORTING

Contact details for reporting SAEs and SUSARs

[contact]

CI email [contact]

Please send SAE forms to: xxx

Tel: xxx (Mon to Fri 09.00 – 17.00)

